## Data Presentation Plan

### Flow chart

Supposing the number of eligible children is  $k$  and the number of excluded children before randomization is  $e$ , with possible reasons for exclusion ( $e_1, e_2, e_3$ ), trial flow chart is shaped as below.

Finally, 30 patients will be randomized in two groups.

If the great majority of the patients will complete the study, we will use a Per Protocol analysis. If many of the randomized patients will not complete the study, we will use an Intention to Treat analysis of data (ITT). According to ITT analysis of data, we will use all the data of all the randomized patients regardless of whether they completed the trial or not. For the missing values we will use the Last Observation Carried Forward (LOCF) approach.

Patient demographics should be similar between the two groups (Table 1). If not, differences will be mentioned and this will be a major limitation of our study.

Intraoperative characteristics (anesthesia duration, pneumoperitoneum duration, IAP, blood loss, administration of crystalloids and / or blood products and intraoperative use of vasoconstrictors should be similar between the two groups (Table 1).

The length of hospital stay and the possible differences between the two groups should be mentioned (Table 1). The number of patients that will develop postoperative pulmonary complications (mainly pneumonia, diagnosed with clinical evaluation and chest radiogram) and possible differences between the two groups should also be recorded.

Pneumothorax and pneumomediastinum would be serious complications, which could have a strong relationship with the RM manipulation, and should be also recorded (see adverse event section above)

**Table 1.** Patient demographics presented as mean (SD) or n = number of patients. Intra- post-operative events presented as mean (SD)

	RM group (n = 15)	Control group (n =15)
Patient Demographics		
Age (years) [mean (SD)]		
ASA (n) [mean (SD)]		
Weight (grams)		
Height (m)		
BMI (kg/m  )		
Sex (male / female)		
Intraoperative characteristics		
Duration of Anesthesia (min)		
Duration of Pneumoperitoneum (min)		
IAP (mmHg)		
Crystalloids (ml)		
Blood (units)		
Need for Vasoconstrictor drugs (n)		
Postoperative characteristics		
Length of Hospital stay (days)		
Pulmonary Complications (n)		
Pneumothorax (n)		
Pneumomediastinum (n)		
Pneumonia (n)		
Other (n)		

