### Exclusion Criteria

Exclusion criteria will be parental or patient refusal, Body Mass Index (BMI) > 40, history of prematurity (birth at post-conceptual age < 37 weeks) or history of congenital lung disorder, clinically recognized airway disease, obstructive or restrictive lung disease, pulmonary hypertension, congenital or acquired heart disease, history of intrathoracic instrumentation, history of severe brain injury and intracranial hypertension.

In addition, all patients who, from the induction of anesthesia until the deflation of pneumoperitoneum, will present any cardiovascular or respiratory major complication (i.e. massive blood loss, arrhythmia, laryngospasm, bronchospasm) will be excluded from the study. In addition, patients will be excluded in case laparoscopy will be converted to open operation due to surgical reasons.

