## Randomization

In order to perform Randomization, the investigators will use web-software-generated blocks (available at: <http://www.randomization.com/>). Patients will be randomized to one of the two Ventilation Management Groups (RM or Control group) with 15 patients per group. Each patient assigned to participate in the study will have a sequentially numbered (from 1 to 30) sealed envelope containing Randomization Code (A or B). The Principal Investigator will be the only person who will be aware of the correspondence between Codes and study Groups. The envelopes will be concealed until deflation of pneumoperitoneum, just prior to application of RM (or not). All operations will be performed by the same team of surgeons and by the same anesthesiologists (PI and Second Investigator). In Appendix 1, there is an example of performed permuted blocks randomization with 30 patients, created by this web-software.

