## Statistical Methods

### Sample size determination

Power Analysis will be conducted for determination of the Sample Size of this study, in order to estimate a Sample Size that is required so that the study would have adequate power to detect clinically meaningful differences between the two groups, especially concerning Lung Compliance (which is the primary outcome of the study).

For this analysis, we used G\*Power Software (version 3.1.9.2), which is freely available at <http://www.gpower.hhu.de/en.html> from the Heinrich-Heine-Universität of Dusseldorf.

Our Power Analysis is based on a published study in literature, from Manner et al. Assuming that Clinically meaningful difference between the two groups is 20% of the mean value and SD of the observed Lung Compliance is 15% of the mean value, therefore Size effect = 0.2 /

0.15 = 1.33, with two-sided testing, with alpha = 0.05 and power = 0.9 (therefore,  $b = 1 - \text{power} = 0.1$ ). Under these assumptions, G\*Power calculated that we will need minimum 13 patients in each group (totally, 26 subjects) for this study to have adequate power.

Assuming a 15% drop-out rate of the initial number of subjects enrolled to this trial, total number of **30** patients will have to be randomized

Alternatively, using the adequate mathematic formula (see Appendix 2) and the results from the Manner et al study, we confirm a minimum Sample Size of 26 patients.

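### The analysis set depends on how many patients complete, with no cut-off; the default set can lose patients from the RM arm only, and LOCF scores a missing RM patient as having no effect

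*Protocol*

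**What the plan says.** The rule stands in the Protocol, Data Presentation Plan, Flow chart. First branch: "If the great majority of the patients will complete the study, we will use a Per Protocol analysis". Second branch: "If many of the randomized patients will not complete the study, we will use an Intention to Treat analysis of data (ITT". After defining ITT as using the data of all randomised patients, the section adds: "For the missing values we will use the Last Observation Carried Forward (LOCF) approach". It does not define completion, give a threshold, name a primary set, or say who decides and when.

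Five other places bear on how the rule works:

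- **Removal of Patients from Therapy** makes haemodynamic instability during the RM the main reason for removal. **Efficacy and Safety Issues** goes further and takes patients with severe instability out of the study, not only off the manoeuvre.
- **Time points of measurements** lists T4c (post-deflation correction) before T5 (3 minutes after the RM). **Appendix 4** has no compliance column after T5.
- **Blinding Procedure** has two investigators analyse the data separately, the principal investigator unblinded, and expects their results to match.
- **Exclusion Criteria** drops "all patients who, from the induction of anesthesia until the deflation of pneumoperitoneum, will present any cardiovascular or respiratory major complication", and also conversions to open surgery.
- **Randomization** says "Each patient assigned to participate in the study will have a sequentially numbered (from 1 to 30) sealed envelope", with the envelopes kept concealed until deflation.

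**The concern.** An analysis set should be fixed before anyone knows how many patients were lost and from which arm. Here it is settled afterwards, by two undefined quantities, with an unblinded analyst involved. Each branch also has its own fault.

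Per protocol, the branch that applies if the trial runs as hoped, drops patients for a reason that cannot occur in the control arm. If children who become unstable during the RM also tend to have lower post-RM compliance, the remaining RM patients look better than the randomised group would have.

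ITT with LOCF keeps the patients but puts the wrong value in the primary outcome. T5 is the only compliance reading after the intervention, so anything carried into it was measured before the intervention. A missing RM patient is then scored as having no RM effect. The primary comparison of a 30-patient trial could therefore be inflated by one branch or diluted by the other.

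**Working it through.** **Inputs from the protocol (Sample size determination, Randomization).** Difference: "Clinically meaningful difference between the two groups is 20% of the mean value". Spread: "SD of the observed Lung Compliance is 15% of the mean value". Test: "with two-sided testing, with alpha = 0.05 and power = 0.9". 15 patients per group.

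**Reproducing the plan's figure.** d = 0.20/0.15 = 1.333. Two-sample t-test, df = n1 + n2 − 2, noncentrality = d/√(1/n1 + 1/n2).

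- 12 + 12: power 0.877
- 13 + 13: noncentrality 1.333 × √6.5 = 3.40, power 0.903. The stated minimum of 13 per group is confirmed.
- 15 + 15: noncentrality 1.333 × √7.5 = 3.65, power 0.941

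**What each branch does when m of the 15 RM patients have no T5.** Assumed, not in the protocol: losses in the RM arm only, m = 2 or 4, T4c–T5 correlation 0.7, SD 15% of the mean at both times, flat control course. With random losses, LOCF gives an expected estimate of 20% × (15 − m)/15:

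- m = 2: 20 × 13/15 = 17.3%
- m = 4: 20 × 11/15 = 14.7%

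Simulation (40,000 runs, two-sided 0.05):

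| Set | RM losses | True effect | Mean estimate | Rejection rate |
|---|---|---|---|---|
| Per protocol | 2, random | 0 | −0.1% | 0.050 |
| Per protocol | 2, lowest T5 | 0 | +3.5% | 0.110 |
| Per protocol | 4, random | 0 | 0.0% | 0.050 |
| Per protocol | 4, lowest T5 | 0 | +6.3% | 0.214 |
| ITT with LOCF | 2, random | 20% | 17.4% | 0.841 |
| ITT with LOCF | 4, random | 20% | 14.7% | 0.675 |
| All 30 observed | none | 20% | 20.0% | 0.94 |

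The lowest-T5 rows are a worst case.

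**LOCF is not always conservative.** If compliance falls 10% from T4c to T5 in both arms, there is no true effect and 4 RM patients are missing, LOCF gives +2.6%. If compliance rises 10%, the true effect is 20% and 4 control patients are missing, LOCF gives 22.7%.

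**Taking whichever set is significant, with no true effect.** Error is 0.063 (m = 2) or 0.070 (m = 4) with random losses, and 0.123 or 0.227 with worst-case losses.

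**Cost of one fixed set.** None in sample size. If T5 were still missing in 4 RM patients at random, 11 + 15 observed gives power 0.896.

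T4c is taken as pre-RM from the order of the time-point table. Blinding Procedure has the second investigator enter after the RM, at T4, which sits awkwardly with that order.

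**The case against.** Several points on the other side have force.

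- **The rule counts completers, not outcomes.** That is so, and nothing says that both sets will be run and the better one kept. A reader might infer that the set will be picked on its result; the text does not say this. The exposure comes from the missing cut-off and timing and the unblinded analyst. Duplicate analysis guards against slips, not against an unfixed choice. With random losses, even picking the better set raises the error only to 0.06–0.07.
- **LOCF most naturally belongs to the ITT branch.** A reader might infer that the planned 15% drop-out already brings LOCF into play. Losing 2 per arm leaves 26 of 30 (87%), which reads most naturally as per protocol without LOCF, with 13 + 13 patients and power 0.903. The same holds for 4 lost from the RM arm alone. The LOCF figures above are therefore conditional on the ITT branch being taken, and the protocol does not say when that is.
- **The Exclusion Criteria losses are a lesser problem.** A reader might infer that complications and conversions before deflation are selective post-randomisation losses, or that depressed pneumoperitoneum values will be carried into T5. The documents do not establish this. Envelopes stay concealed until deflation and management is the same until then, so these losses should not differ by arm. The Flow chart section provides for exclusions before randomisation, while Randomization gives each assigned patient a numbered envelope. Which applies is ambiguous. The protocol also gives no size for a compliance fall in such patients.
- **A separate SAP may exist.** It could not repair this without contradicting the rule that the protocol states.

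**Conclusion.** The rule is wrong as written and should be changed before data are seen. The wording defect is certain: no cut-off, no named primary set, a default set open to removals that can arise only in the RM arm, and LOCF replacing the sole post-RM reading with a pre-RM value.

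The size is not certain. The protocol gives no expected number of RM-related removals, and the figures rest on the assumed loss counts, the correlation of 0.7 and, for per protocol, worst-case selection. On those terms, type I error under per protocol is about 0.11 to 0.21 instead of 0.05. If the ITT branch is taken, LOCF removes 20/15 = 1.3 percentage points of a true 20% effect for each missing RM patient. If losses are unrelated to outcome, per protocol is unbiased and loses only some power.

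**What to change.** 1. **Flow chart section:** name one primary set in advance: every patient whose envelope was opened, analysed in the assigned group whether or not the RM was completed. Keep per protocol as supportive only.
2. **Same section:** delete LOCF. Analyse observed T5; if any T5 is missing, use a likelihood-based mixed model or multiple imputation, with a sensitivity analysis.
3. **Removal of Patients from Therapy and Efficacy and Safety Issues:** reconcile the two, since one speaks of removal from therapy and the other of removal from the study. For the analysis, stopping the RM should not end data collection, and T5 should still be recorded where possible. The clinical criteria and management are not touched.
4. **Randomization:** state that the envelope number is assigned at deflation, after the Exclusion Criteria have been applied, so that those losses clearly precede randomisation.

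The cost is wording in several sections and a change in when the number is written down. A few more children may need to be consented to use all 30 envelopes. The sample size stands.

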### Results and Discussion

Data will be presented as mean value (+/- SD) and  $p < 0.05$  will be considered significant. The investigators will use Mixed Analysis of Variance to make comparisons between and within groups. At time points before RM is performed, there should be no significant differences in Lung Compliance between the two groups ( $p > 0.05$ ). The investigators will use two-sample t-test as supplementary analysis in order to compare the two groups at each time point, while chi-square test for categorical variables and two-sample t-test for continuous variables for patient and procedural characteristics differences between the two groups will be used. In the RM group, according to similar studies, we expect to detect a significant increase in lung Compliance after RM in comparison to control group where RM will not be applied. In the RM group, the investigators estimate that Dynamic Lung Compliance will be significantly increased compared to baseline compliance too. There should be no significant differences in demographics between the two groups. The investigators expect that there will be no statistical or/and clinical significant differences in patients' hemodynamics and blood gas measurements.

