### Statistical Analysis

[figure not shown]
Investigators will assess data for normality (using Kolmogorov Smirnov and Shapiro Wilks test). Ventilatory and hemodynamic data and intraoperative and postoperative variables (all continuous variables) will be presented as mean values (+/- SD). Data will be compared between and within groups using Mixed Analysis of Variance (Mixed Anova - General Linear Model) if are normally distributed or with Kruskal Wallis test in case that we do not have normally distributed data. Bonferroni correction will be used for multiple comparisons correction. In order to check and supplement our Mixed Analysis of Variance we will also use two-sample t-test to compare the two groups at each time point (for ventilatory and hemodynamic variables). Patient and procedural characteristics will be compared between groups using independent-sample t-test for continuous variables and chi-square test for categorical variables. Two tailed P-values < 0.05 will be considered statistically significant. For data analysis, the investigators will use SPSS statistical software (version 22).

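### Randomised groups are to be significance-tested on demographics, with dissimilarity labelled a major limitation: a rule that fires by chance in about 14–26% of sound trials and misses moderate imbalance

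*Protocol*

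**What the plan says.** Three places in the protocol bear on this.

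- **Statistical Analysis** plans the tests: "Patient and procedural characteristics will be compared between groups using independent-sample t-test for continuous variables and chi-square test for categorical variables". The threshold is general: "Two tailed P-values < 0.05 will be considered statistically significant".
- **Abstract, Results and Discussion** states the expected outcome: "There should be no significant differences in demographics between the two groups". It sets the same kind of expectation, with p above 0.05, for lung compliance at the time points before the recruitment manoeuvre (RM).
- **Data Presentation Plan, Flow chart** says that demographics should be similar between the groups, and continues: "If not, differences will be mentioned and this will be a major limitation of our study". The next paragraph says that intraoperative characteristics should also be similar, but attaches no consequence.

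The Randomization section gives the size: "Patients will be randomized to one of the two Ventilation Management Groups (RM or Control group) with 15 patients per group". The envelope stays sealed until deflation of the pneumoperitoneum. No covariate-adjusted analysis is stated; weight enters only by dividing compliance by it.

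**The concern.** A significance test on a baseline variable asks whether the difference is larger than chance would produce. When groups are formed at random and the variable is fixed before allocation is revealed, chance is already known to be the explanation. A small p-value is then a false alarm. A large one, with 15 children per arm, says little about whether the groups are alike.

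The protocol nevertheless ties a reporting consequence to dissimilar demographics. Because it defines similarity nowhere else, its authors are likely to fall back on the planned tests. A sound trial may then carry a self-declared major limitation for no reason, while a moderate imbalance that could matter goes unremarked.

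Prognostic imbalance is a fair worry here. The Limitations section itself says that the children differ widely in age and size, and that age-related factors may affect compliance even after weight correction. The stated response to a demographic imbalance is only to mention it.

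**Working it through.** **Inputs from the protocol.** Two-sided alpha is 0.05 and there are 15 children per arm. Table 1 has six demographic rows (age, ASA class, weight, height, BMI, sex). The SD of compliance is 15% of the mean and the target difference 20% of the mean (Sample size determination).

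**The plan's own figure.** The protocol gives no false-alarm rate for the baseline tests. Its sample size reproduces: with effect size 0.20/0.15 = 1.33, a two-sample t-test has power 0.877 with 12 per group and 0.903 with 13, hence 26 in total.

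**1. False alarms over the six rows, with perfect randomisation.**
- Independent rows: 1 − 0.95^6 = 0.265. This is close to the maximum.
- The rows are not independent: BMI is computed from weight and height, and weight and height follow age. With the four continuous rows equally correlated (assumed) and sex and ASA independent:

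| Assumed correlation | At least one p<0.05 |
|---|---|
| 0 | 26.5% |
| 0.5 | 23.9% |
| 0.7 | 21.5% |
| 0.8 | 20.0% |
| 0.9 | 18.3% |

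- An illustrative paediatric simulation (40,000 trials) gave 19.7%. It assumed age uniform over 1–14 years, height rising with age, BMI scattered around an age-dependent value, weight derived from both, equal sexes and 25% ASA 2.
- The same simulation with a continuity-corrected chi-square gave 13.8%. The protocol does not say which chi-square is meant.

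The supported range is therefore about 14–26%.

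**2. What the test can detect with 15 per arm (continuous rows).**
- Smallest significant standardised difference: t(0.975; 28 df) × √(2/15) = 2.048 × 0.365 = 0.75 SD. An observed difference below this is never flagged.
- Power against a systematic difference: 12% at 0.3 SD, 26% at 0.5 SD, 56% at 0.8 SD.
- Chance alone gives an observed difference above 0.5 SD in 18% of trials for each variable.

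**3. What an imbalance could do to the compliance comparison.** Assume a correlation of 0.7 between T4c and T5 compliance (not a protocol figure), equal SDs, and a T4c imbalance of 0.5 SD.
- Unadjusted T5 t-test: expected shift 0.7 × 0.5 × 15% = 5.25% of the mean, about a quarter of the 20% target.
- T4c-to-T5 change: (0.7 − 1) × 0.5 × 15% = −2.25%, smaller and in the opposite direction.
- ANCOVA on T4c removes the expected shift.

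Relative residual variance under the same assumption: 1.00 for the T5 t-test, 2 × (1 − 0.7) = 0.60 for the change, and 1 − 0.7² = 0.51 for ANCOVA.

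**The case against.** **Similarity is not defined as p>0.05.** True. The Flow chart section mentions no p-value; the link is an inference from the Abstract and Statistical Analysis. It is a reasonable one, since no other criterion appears. A reader might also infer that a non-significant test is to be taken as proof of similarity. The protocol does not say so; it states an expectation.

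**All of Table 1 is covered.** A reader might count the six intraoperative rows as well and quote 1 − 0.95^12 = 46%. The documents do not support that. The consequence is written for demographics only. Twelve rows would not be independent either (the same simulation gave about 25–31%). Some of those rows, such as anaesthesia duration and vasoconstrictor use, can be affected after the envelope is opened, so comparing them is not baseline testing.

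**Bonferroni would cure it.** If applied to the six rows, the false-alarm rate would be 1 − (1 − 0.05/6)^6 = 4.9%. But that sentence follows the Mixed ANOVA and precedes the baseline tests, and is not stated to cover Table 1. It would also make moderate imbalances still harder to flag.

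**The main analysis already uses pre-RM values.** This stands in part. The Mixed ANOVA works on repeated measurements, and its group-by-time term compares changes, so a constant offset drops out. It would be wrong to infer that imbalance is left wholly uncorrected or that the primary estimate is spoiled. The 5% shift belongs to the T5 t-test, which the protocol calls supplementary.

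**Differences may not be pure chance.** Children can be excluded between induction and deflation or removed during the RM, and the analysis may be per protocol. The analysed groups may then differ from the randomised ones. That is a reason to show imbalances openly, by size. With 15 or fewer per arm, a p-value would not detect such selection reliably.

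**Conclusion.** The point holds at the level of wording and interpretation. The protocol plans significance tests of randomised groups on demographics and labels dissimilarity a major limitation, with significance as the only criterion on offer. On that reading, about 14–26% of properly randomised trials would attract the label by chance. The range rests on assumed correlations among age, weight, height and BMI and on the choice of chi-square; 26.5% assumes independence. A systematic 0.5 SD difference would be flagged only about 26% of the time.

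A reader might go further and say that the rule changes the trial's conclusion. It does not: no analysis, population or decision depends on the sentence, which commits the authors to a comment in the report. The only numerical exposure is in the supplementary T5 t-test: about 5% of the mean for a 0.5 SD pre-RM imbalance, if the correlation is 0.7. The point is minor but cheap to correct.

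**What to change.** 1. In Statistical Analysis and Table 1, present the six demographic rows descriptively, without p-values.
2. Replace the major-limitation sentence, and the Abstract's expectations of no significant difference in demographics and in pre-RM compliance, with a statement that imbalances will be described by their size. This keeps the disclosure and drops the test.
3. Prespecify the T5 group comparison of weight-corrected compliance as an ANCOVA adjusted for the same child's T4c value, in place of the unadjusted T5 t-test. Confirm in the text that T4c is read before the RM: the Time points table implies this, but the Blinding Procedure has the second investigator enter after the RM, at T4.
4. Keep between-group comparisons for rows that can be affected after the envelope is opened, such as vasoconstrictor use and anaesthesia duration.

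The cost is wording and one model degree of freedom. T4c is already recorded for every child in Appendix 4, so no patients, visits or measurements are added. At an assumed correlation of 0.7 the ANCOVA also reduces residual variance to about half that of the T5 t-test.

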## End of Treatment

The treatment (RM) will start 3 minutes after the Pneumoperitoneum deflation and will last for 30 seconds.

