Because of the transient increase in intrathoracic pressure and consequent reduction in venous return, cardiac output may be impaired, producing hypotension – a complication that appears to be more common in patients with poor chest wall compliance and limited oxygenation response from recruitment. Generally, hypotension during the maneuver suggests relative volume depletion. In this study, RM will be performed with a parallel beat-to-beat hemodynamic monitoring (Invasive Arterial Blood Pressure Monitoring). Patients with severe hemodynamic instability (hypotension or arrhythmias) will be removed from the study, as already mentioned. In these patients, the removal of RM is expected to improve arterial blood pressure – in case hypotension persists, vasoconstrictors (ephedrine, norepinephrine) will be administered in adequate for each patient doses.

A decrease in cerebral perfusion pressure has been noted as a RM complication, which may contraindicate this procedure in head injured patients. In this study, patients with history of severe brain injury and intracranial hypertension meet the exclusion criteria and will be excluded.

Barotrauma, including pneumothorax and pneumomediastinum, has been also described but the exact risk remains unclear. Nevertheless, when RM is performed with the duration and the pressure levels adopted in this study (Sustained Inflation with CPAP 30 mm  $H_2O$  for 30

seconds) is thought to be a safe clinical maneuver without such major complications to children

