## Adverse Events

In addition to RM complications (see above), any perioperative adverse event will be recorded, such as laryngospasm, bronchospasm, pneumothorax, subcutaneous emphysema, hypotension, bradycardia, desaturation ( $\text{SPO}_2 < 92\%$ ) or hypercapnia ( $\text{PaCO}_2 > 45 \text{ mmHg}$ ).

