### Appendix 3 - Demographic intra- & post-operative patient's data

Patient ID	
Age (years)	
ASA (n)	
Weight (grams)	
Height (m)	
BMI (kg/m  )	
Sex (male / female)	
Type of Surgery	
Duration of Anesthesia (min)	
Duration of Pneumoperitoneum (min)	
IAP (mmHg)	
Crystalloids (ml)	
Blood (units)	
Need for Vasoconstrictor drugs (n)	
Length of Hospital stay (days)	
Pulmonary Complications (n)	

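### Vasoconstrictor use, a possible harm of the recruitment manoeuvre, is listed as a background characteristic expected to match and is recorded in one untimed field

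*Protocol*

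**What the plan says.** Efficacy and Safety Issues explains that during the RM "cardiac output may be impaired, producing hypotension". If stopping the manoeuvre is not enough, "in case hypotension persists, vasoconstrictors (ephedrine, norepinephrine) will be administered in adequate for each patient doses".

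The presentation plan (Flow chart, under Data Presentation Plan) puts the same item in a list with anesthesia duration, pneumoperitoneum duration and IAP, and says that "administration of crystalloids and / or blood products and intraoperative use of vasoconstrictors should be similar between the two groups". Table 1 places it under intraoperative characteristics. That section singles out only pneumothorax and pneumomediastinum as complications that may be tied to the RM.

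Appendix 3 collects the item in a single row beginning "Need for Vasoconstrictor drugs (n", with no time column. Crystalloid volume is also one figure per patient.

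On timing, End of Treatment states: "The treatment (RM) will start 3 minutes after the Pneumoperitoneum deflation and will last for 30 seconds". Until then the arms receive the same management (Interventions & Treatments), and the envelopes stay closed until deflation (Randomization).

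**The concern.** A drug given because the intervention lowered blood pressure is a consequence of treatment. The plan lists it with items that describe how comparable the two operations were, and states in advance that the arms ought not to differ on it.

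The form adds a second problem. Most of the operation precedes a 30-second manoeuvre, and nothing given before it can be an RM effect. The section on hemodynamics during laparoscopy names hypotension among the changes to expect, so some use before the RM is foreseeable. One untimed count mixes that use with whatever follows the RM. An analysis plan written later cannot restore timing that the form did not capture, so this belongs in the protocol.

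At stake is one of the clearest safety contrasts in a trial that its Brief description calls a safety and efficacy study. No primary or gas-exchange endpoint is affected.

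**Working it through.** **The plan's own figures.** The protocol gives no expected rate of vasoconstrictor use, so there is no figure to reproduce on this point. The sample size concerns compliance only: with d = 1.33 and two-sided alpha 0.05, 13 per arm gives power 0.902, as stated. Nothing below changes it.

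**Inputs from the protocol.** 15 per arm (Randomization); chi-square test for categorical characteristics, two-tailed 0.05 (Statistical Analysis).

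**Assumptions.**
- The field counts children who received any vasoconstrictor.
- b is the proportion treated before the RM, equal in both arms: 0, 20% or 40%.
- The post-RM risk r is 2% in controls and 10% to 40% in the RM arm.
- Use before and after the RM is independent within a child.

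**Formula.** Whole-operation risk = b + (1 − b)r. The difference between arms is therefore (1 − b)(r_RM − r_control).

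Example with r_RM = 20% and b = 20%:
- RM arm: 0.20 + 0.80 × 0.20 = 0.360
- Control arm: 0.20 + 0.80 × 0.02 = 0.216
- Difference: 0.144, against 0.20 − 0.02 = 0.18 when only post-RM use is counted
- Ratio: 0.360 / 0.216 = 1.7, against 0.20 / 0.02 = 10

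**Power.** Exact enumeration of all outcomes at 15 per arm, Pearson chi-square without continuity correction:

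| RM-arm post-RM rate | b = 0 | b = 20% | b = 40% |
|---|---|---|---|
| 10% | 0.04 | 0.07 | 0.05 |
| 20% | 0.27 | 0.15 | 0.08 |
| 30% | 0.59 | 0.27 | 0.14 |
| 40% | 0.82 | 0.42 | 0.23 |

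Fisher's exact test gives lower values: in the 40% row, 0.67, 0.25 and 0.12.

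**A concrete table.** Suppose four RM children and no controls need a vasoconstrictor after the RM. For 4 v 0 of 15, chi-square p = 0.032 (Fisher 0.100). Add three other children per arm treated only before the RM. The recorded result is 7 v 3, with chi-square p = 0.121 (Fisher 0.245). The RM effect is the same in both tables.

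**The case against.** The strongest reply is that hemodynamic safety does not rest on this one row.

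- Blood pressure and heart rate are recorded at T4c, T5 and T6 (Appendix 5), and hemodynamic variables are to be compared between arms at each time point.
- The RM is done under beat-to-beat arterial monitoring, and an independent DMC may see unblinded data.
- The Adverse Events section covers RM complications as well as other events: "any perioperative adverse event will be recorded, such as laryngospasm, bronchospasm, pneumothorax, subcutaneous emphysema, hypotension, bradycardia, desaturation" and so on.

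All of this stands and limits the loss. It does not close the gap. T5 is 3 minutes after the RM and can miss a brief episode or one already treated, which is when a drug record is most informative. The Adverse Events section gives no time field either.

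A second reply is that pre-RM use will be rare. Patients are ASA 1–2, and those who between induction and deflation have "any cardiovascular or respiratory major complication (i.e. massive blood loss, arrhythmia, laryngospasm, bronchospasm) will be excluded from the study". That lowers b, but the examples name neither hypotension nor vasoconstrictor use. It is also fair to say that a 40% RM rate is extreme, since the protocol describes recruitment as generally well tolerated. At 10% the trial could not detect the difference however it was counted.

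Two stronger readings are tempting, and the protocol supports neither.

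- **That an excess in the RM arm would be dismissed as chance imbalance.** The sentence that calls a difference a major limitation concerns demographics only. The row is still shown by arm, with a planned test.
- **That hypercapnia before and after the RM could not be told apart.** Appendix 6 has blood gases at T4c and T5, so new hypercapnia can be derived.

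**Conclusion.** The point holds in a limited form. By the protocol's own account, vasoconstrictor use from the RM onward may be a harm of the intervention. The plan lists whole-operation use among characteristics expected to match, and its form cannot separate the two periods.

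The direction of the effect follows from arithmetic: any b above zero shrinks the risk difference by (1 − b). The size is illustrative, because every rate is assumed. For RM rates of 20% to 40%, a pre-RM rate of 20% cuts power by roughly half. At 10% power is below 0.08 throughout.

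A reader might infer that the trial would declare the RM hemodynamically safe against its own data. That does not follow, given the timed blood pressure comparisons and adverse-event recording. This is a cheap improvement to safety reporting and is best made before enrolment, because unrecorded timing may not be recoverable.

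**What to change.** 1. **Appendix 3:** split vasoconstrictor use and crystalloid volume into before RM start and from RM start onward. In controls, use the matching time after deflation. RM start is a safer anchor than a T label, because Blinding Procedure refers to T4 for recording after the RM, whereas the time-point table puts the post-RM reading at T5.
2. **Table 1 and Flow chart text:** keep the pre-RM part under intraoperative characteristics. Move the part from RM start to a safety block by arm, and take it out of the list of items expected to match.
3. **Population:** report that block for all randomized patients. The protocol says "Patients with severe hemodynamic instability (hypotension or arrhythmias) will be removed from the study, as already mentioned" and defaults to a per-protocol analysis when most patients complete, so the children most likely to have needed a vasoconstrictor could otherwise be left out of the table.
4. **Adverse events:** mark each event as before or after the same point.

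The cost is an extra column on one form, a time mark on each adverse event and a regrouped table. Staff must note when each drug was given or event occurred relative to the RM. No change is needed to sample size, procedures or clinical management.
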